6.9 Financing

6.10 Reference code of ethics

6.11 Subjects' insurance

7. PREMATURE INTERRUPTION OF THE STUDY

8. GLOSSARY

9. ANNEXES TO THE CLINICAL INVESTIGATION PLAN

10. BIBLIOGRAPHY

1. SYNOPSIS

TITLE	Evaluation of the performance and safety of a type I collagen medical device (MD Shoulder Collagen Medical Device) in the treatment of rotator cuff syndrome. " Ropiramed pilot study "
STUDY DESCRIPTION	This single-centre pilot clinical investigation will be based on a one-sample design. Variables will be assessed at 6 different times: at baseline (day 0), after weeks 2, weeks 4, months 3, months 6 and after months 12 i.e. 11 months after the end of the infiltrative treatment.
OBJECTIVES	The objective of this study is to evaluate, the performance of an intra-articular treatment with a collagen-based medical device in recovering joint function and reducing associated pain. The safety of the treatment will also be evaluated.
PRIMARY ENDPOINT	The primary End Point will consist of evaluating, by means of the Constant-Murley Functional Scale (CMS), the effectiveness, in terms of performance, of the MD-Shoulder Collagen Medical Device in recovering joint function and reducing pain associated with time T3 months. An increase of at least 13 points on the CMS scale is considered clinically significant.
POPULATIONS	A total of 24 subjects suffering from rotator cuff syndrome will be enrolled.
SELECTION CRITERIA	
Inclusion Criteria:
 
• Subjects aged > 18 years.• Subjects with shoulder pain for at least 3 month.• Subjects with a diagnosis of rotator cuff tendinopathy, subacromial conflict syndrome, partial rotator cuff tendon lesions (lesions A and B according to Snyder's Classification).• Subjects with a CMS score between 40 and 75.• Subjects who understood and signed the Informed Consent to Active Participation in the study.• Subjects capable of understanding the terms of the study and participating throughout. 
Exclusion Criteria:

	
• Subjects with complete rotator cuff lesions (C lesions according to Snyder's classification).• Subjects with shoulder instability.• Subjects with adhesive retractile capsulitis.• Subjects undergoing HA and/or cortisone infiltration in a period < 3 months.• Subjects with diabetes mellitus.• Subjects with uncontrolled thyroid disease.• Subjects with coagulopathies.• Subjects on chronic treatment with immunosuppressants.• Persons with an allergy to porcine collagen.• Subjects who are pregnant or breastfeeding.
STUDY PHASE	Fase IV post market
NUMBER OF CENTRES	1 Experimental Center.
DESCRIPTION OF THE MEDICAL DEVICE UNDER STUDY	MD-Shoulder Collagen Medical Device is an injectable medical device based on porcine collagen type I; the collagen content is 100µg/2mL.
STUDY DURATION	The total duration of the Clinical Investigation will be 16 months. There will be a 4-month subject selection and recruitment period and a 12-month treatment and observation period.
STUDY DURATION PER SUBJECT	The duration of the study for each subject will be 12 months.

1. LIST OF ABBREVIATIONS

AE	Adverse Event
ASES	American Shoulder and Elbow Surgeons
CMS	Constant-Murley Score
COL-1	Collagen type I
E-CRF	electronic Case Report Forms
NSAIDs	Non-steroidal anti-inflammatory drugs
GCP	Good clinical practice
HA	Hyaluronic Acid
ICH	International Council for Harmonisation of Technical Requirements for Pharmaceuticals for Human Use
MD	Medical Device
NRS	Numeric Rating Scale
MR	Magnetic resonance
ROM	Range of Motion
RCS	Rotator Cuff Syndrome
SAE	Evento Avverso Serio
SST	Serious Adverse Event
SUSAR	Suspected Unexpected Serious Adverse Reaction

2. INTRODUCTION

2.1 Anatomical background on the rotator cuff

The rotator cuff is an anatomical structure consisting of the tendons of four muscles that originate at the level of the scapula and insert on the proximal humerus, these deep muscles of the shoulder: supraspinatus, subspinatus, subscapularis, and the small round provides rotational movements to the shoulder [1]. The supraspinatus muscle originates from the supraspinous fossa of the scapula to insert on the upper face of the trochis and together with the deltoid, acts as the motor muscle of scapulohumeral abduction. The supraspinatus muscle holds the head of the humerus against the glenoid cavity, preventing upward dislocation of the head of the humerus otherwise caused by the action of the deltoid [2]. The subspinatus muscle, external rotator of the shoulder, originates from the subspinous fossa of the scapula and inserts on the postero-superior aspect of the trochitis. The subscapularis muscle, internal rotator of the shoulder, originates from the scapular fossa and inserts on the trochine. Finally, the small round muscle, external rotator of the shoulder, originates from the inferior part of the subspinous fossa and inserts on the postero-inferior face of the trochis. This muscle complex has the important role of stabilizing the glenohumeral joint and counteracting the luxating action of the deltoid. By contracting, in fact, these muscles produce a downward force that perfectly opposes the opposite action of the deltoid, creating a rotational torque generating abduction (ivi). All four rotator cuff muscles join the scapula to the humerus, enveloping the glenohumeral joint; their tendons cover the capsule and fuse with it, playing an important role in preserving joint integrity [3]. These muscles are also referred to as transverse stabilizers of the shoulder because, through them, the head of the humerus is stabilized and maintained on the glans of the scapula.

2.2 Tendinopathy and rotator cuff injuries

Rotator cuff tendinopathy is a commonly encountered musculoskeletal disorder in clinical practice, with an incidence ranging from 0.3% to 5.5%, and an annual prevalence of 0.5% to 7.4% [4]. Furthermore, over time, at a monthly rate of 0.26%, this condition can progress to complete rotator cuff tendon injury resulting in worsening pain and shoulder function [5].

The etiology of rotator cuff tendinopathy is still controversial. Some authors believe that it is an expression of a primary extrinsic compression due to a reduction of the sub-acromial space, while others attribute this pathology to an intrinsic degeneration of the tendons with a consequent development of secondary impingement. In this case, the hypothesis is that an altered microcirculation of the shoulder tendons leads to weakness of the rotator cuff resulting in rising humeral head and compression of the overlying structures. What we do know is that in tendinopathies there are histologic changes in the structure of the tendons, which include increased glycosaminoglycans and proteoglycans content, remodeling of collagen fibers, hypercellularity, neovascularization, and changes in the extracellular matrix pattern with increased noncollagenous components. These cellular

and molecular alterations result in a change in the mechanical properties of tendons and lead to a chronic, often disabling pain condition [6].

Although conservative therapy should still be considered the first choice in cuff tendinopathy, the clinical results of the various types of nonsurgical treatments are still mixed and often show poor efficacy.

Numerous studies identify exercise as the most viable therapeutic option in the treatment of rotator cuff tendinopathy, although the amount and type of potentially optimal exercise has not yet been defined. In addition, physiotherapy does not seem to be able to change the natural history of this pathology.

This explains the growing interest of the scientific community in developing new biological therapies that can both improve shoulder function and promote tendon healing.

Among the most studied biologic therapies in rotator cuff tendinopathies, platelet-derived growth factors (Platelet-rich Plasma, PRP) appear to be the most widely used in clinical practice because they are easy to prepare, yet they present mixed clinical results. In contrast, mesenchymal stem cells have shown promising results, especially in vitro, but require invasive harvesting systems and the need to expand the cells ex vivo before they can be injected at the site of tendon injury. [7]

2.3 Pre-clinical studies

Recently, F. Randelli et al. studied the in vitro effects on tenocytes induced by *MD-Tissue Collagen Medical Device*, an injectable, ready-to-use, porcine collagen-based medical device (100 g/2 mL vials) [8].

In vitro results appear to demonstrate that *MD-Tissue Collagen Medical Device* can induce tenocyte proliferation and migration and type I collagen synthesis, maturation, and secretion, promoting tendon repair. [8]

F. Randelli et al. also demonstrated the purely mechanical activity of *MD-Tissue Collagen Medical Device*, which is able to induce changes in the morpho-functional properties of tenocytes. [9]

The aim of our study is to evaluate, by means of the Constant & Murley functional scale [Constant-Murley Score (CMS)], the performance of intra-articular treatment with a collagen-based medical device (*MD-Shoulder Collagen Medical Device*) in recovering joint function and reducing pain in rotator cuff tendinopathy.

3. SCIENTIFIC REQUIREMENTS

3.1 Study title

Evaluation of the performance and safety of a type I collagen medical device (*MD-Shoulder Collagen Medical Device*) in the treatment of rotator cuff syndrome. "Ropiramed pilot study"

3.2 Purpose of the clinical study

The purpose of this clinical study is to evaluate, through the CMS functional scale, the performance of intra-articular treatment with a collagen-based medical device in recovering joint function and reducing associated pain. The safety of the treatment will also be evaluated

3.3 Clinical study Design

This single-center pilot Study Clinical Investigation will be based on a One sample design. Variables will be assessed at 6 different times: at baseline (T0 time), after 2 weeks (T2w), after 4 weeks (T4w), after 3 months (T3months), after 6 months (T6/FU), and after 12 months (T12/FU) i.e., 11 months after the end of infiltrative treatment.

3.4 Duration of the Clinical Study

The total duration of the clinical study will be 16 months. There will be a subject selection and recruitment period of 4 months and a treatment and observation period of 12 months. (See Figure 1).

[figure not shown]

Fig.1 Flow chart of the clinical study design

3.5 Participating population

A total of 24 subjects with painful shoulder in rotator cuff tendinopathy will be enrolled. The recruitment phase will be closed no earlier than the number of subjects stipulated in the Clinical Investigation Plan has been reached.

Only subjects will be included:

- belonging to the U.O.C. 1st Orthopedic Clinic (Gaetano Pini Orthopedic Institute, Milan, Italy);
- who meet the inclusion criteria and have no exclusion criteria.

3.6 Enrollment

Enrollment will begin only after approval of the Clinical Investigation Plan by the ASST Istituto Ortopedico Gaetano Pini Ethics Committee and notification of the study at the Ministry of Health.

Enrollment will involve subjects with rotator cuff syndrome who are eligible according to the selection criteria. Diagnosis will be performed by the Principal Investigator through clinical examination and instrumental investigation with shoulder MRI. The MRI examination must be recent and of good quality; if the subject does not have it, an MRI examination will be performed before diagnosis and enrollment. Eligible subjects will be explained by the Co-Investigator the rationale for the Clinical Investigation Plan and the procedures involved. Consent to participate in the study will then be sought.

3.6.1 Selection Criteria

3.6.2 Inclusion Criteria

- Subjects with age > 18 years;
- Subjects with shoulder pain for at least 3 month;
- Subjects with a diagnosis of rotator cuff tendinopathy, subacromial conflict syndrome, partial rotator cuff tendon injuries (injuries A and B according to Snyder's Classification);
- Subjects with a CMS score between 40 and 75;
- Subjects who understood and signed the informed consent for active participation in the study;
- Subjects who are able to understand the conditions of the study and take part throughout the duration of the study.

3.6.3 Exclusion Criteria

- Subjects with complete rotator cuff injuries (C injuries according to Snyder's classification);
- Subjects with shoulder instability;
- Subjects with adhesive retractile capsulitis;
- Subjects undergoing HA and/or cortisone infiltration in a period < 3 months;
- Subjects with diabetes mellitus;
- Subjects with uncontrolled thyroid disease;
- Subjects with coagulopathies;
- Subjects on chronic treatment with immunosuppressants;
- Subjects with allergy to porcine collagen;
- Subjects in pregnancy or lactation.

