4.9.2 Plan Visits

T0 BASAL: Enrollment

During the daily clinical activity, investigators participating in the Investigation will select subjects with rotator cuff syndrome. The Principal Investigator will be responsible for the correct clinical diagnosis by also making use of the instrumental examinations provided in the Investigation Plan. Subjects meeting the selection criteria will thus be identified. After fully explaining the purposes, aims and procedures stipulated in the Clinical Investigation Plan, the subject will be offered participation in the Clinical Investigation Plan itself. Finally, the selected subject will be asked to review the information form and to date and sign the Informed Consent and Consent to Processing of Personal Data form.

Female subjects will need to provide evidence of a negative pregnancy test in order to be enrolled.

We will then proceed with the objective examination and collection of the information required by the appropriately prepared Electronic Data Collection Form.

This will be followed by:

- CMS assessment;
- NRS assessment;
- ASES assessment.
- SST evaluation;
- shoulder ROM evaluation;
- MRI evaluation.

The first infiltration will then be performed via ultrasound.

Previous or ongoing pharmacological treatments of any kind will be documented.

In order to monitor the consumption of analgesic (Celecoxib 200mg / Paracetamol 1000 mg) used during the Clinical study in case of pain onset, a clinical diary will be given to the subject in which to indicate the day and dose of medication used.

The enrolled subject will be given the identification code formed by the progressive enrollment number followed by an alphanumeric code.

T2 week (±2 days):

At 14 days from day 0 (enrollment), the second infiltration will be performed through echoguide and pain assessment through NRS, finally painkiller drug use will be evaluated through clinical diary analysis, and any Adverse Events occurred after the first administration will be assessed.

T4 weeks (±2 days):

At 28 days from day 0 (T4w), the third ultrasound-guided infiltration and pain assessment through NRS will be performed, finally painkiller drug use will be assessed through clinical diary analysis and any Adverse Events occurred after the last administration will be evaluated.

T3 months (±7 days):

At 3 months from day 0 and at 2 months from the last echoguided administration, the End Points in the Clinical Investigation Plan will be assessed.

Including:

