4.11 Study group

Only one experimental group is included in the investigation plan, which will be treated with 2 ml volume ultrasound-guided infiltrations of MD-Shoulder *Collagen Medical Device* (GUNA, Milan-Italy). Composition per 2 ml: collagen 100 micrograms.

Excipients: Iris, NaCl, Water for injection. Subjects will be treated with no. 1 ultrasound infiltration at the time of enrolment, 2 weeks after enrolment and 4 weeks after enrolment.

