4.13.1 Effectiveness Criteria

4.13.2 Primary End Point

The primary End Point will consist of the evaluation, by means of the Constant-Murley Functional Scale (CMS), of the effectiveness, in terms of performance, of MD-Shoulder *Collagen Medical Device* in the recovery of joint function and reduction of associated pain at time months 3, i.e. 3 months after the first infiltration, compared to baseline (day 0). An increase of at least 15 points on the CMS scale is considered clinically significant.

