5.2.2 Primary Endpoint

The primary endpoint will be assessed by Student's t-test for paired data as already established in the section on sample size.

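### The prior-injection exclusion names only HA and cortisone, so any residual effect of a recent PRP or collagen injection is confounded with the 3-month CMS change, in either direction

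*Combined protocol and SAP*

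**What the plan says.** Section 3.6.3 excludes "Subjects undergoing HA and/or cortisone infiltration in a period < 3 months", and the synopsis has the same rule. No other criterion deals with an earlier injection. The only criterion that mentions collagen concerns allergy: "Subjects with allergy to porcine collagen".

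The plan gives two reasons to expect other injectables in this population. Section 2.2 says of platelet-derived products, among the most-studied biologics, that they "appear to be the most widely used in clinical practice because they are easy to prepare"; the same sentence adds that their clinical results are mixed. The synopsis gives the study phase as "Fase IV post market".

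On treatment history, the T0 visit in section 4.9.2 states: "Previous or ongoing pharmacological treatments of any kind will be documented". Table 1 also has a general history-taking row at T0.

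On design, section 4.11 states: "Only one experimental group is included in the investigation plan". The primary endpoint in section 4.13.2 is CMS at 3 months against day 0, and section 5.2.2 states: "The primary endpoint will be assessed by Student's t-test for paired data". No covariate, subgroup or sensitivity analysis by prior treatment is planned.

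**The concern.** By excluding recent HA and cortisone, the plan accepts that an earlier injection can disturb the 3-month result. It gives no reason for stopping at those two products. A patient who received PRP or a collagen device in the same shoulder two weeks before day 0 breaks no criterion. Patients come from an orthopaedic clinic and have had pain for at least 3 months, so earlier treatment is plausible.

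A randomised control arm would, on average, carry the same mix of earlier treatments, and the comparison between arms would remove it. Here there is no such arm. Every change in CMS after day 0, whatever its cause, enters the estimate and is read as device performance.

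The T0 record may not reveal the problem. The plan's own glossary defines a medical device as something whose principal action is not pharmacological, so a line about pharmacological treatments need not capture an earlier device injection, and it is unclear whether it captures PRP.

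**Working it through.** **Inputs from the documents.** N = 24, planning difference 13, SD of differences 20, stated power 86.2% (section 5.1); one group (section 4.11); month 3 versus day 0 (section 4.13.2); paired t-test (section 5.2.2). Alpha and sidedness are not stated; 0.05 two-sided is assumed.

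**The plan's own figure.** Noncentrality = (13/20) × √24 = 3.18 with 23 degrees of freedom. The noncentral t distribution gives a power of 86.19%, which agrees with the stated 86.2%. The point disputes no figure in the sample-size section.

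**What the paired difference measures.** Let D be the device effect at 3 months and R(t) the residual effect of an earlier injection on CMS at time t. If the two add, a patient's measured change contains D + R(3 months) − R(0). The carry-over term is c = R(3 months) − R(0).

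- Benefit still building, for example R going from 0 to 10: c = +10, and the gain is overstated.
- Benefit stable, for example R at 10 on both occasions: c = 0, and it cancels.
- Benefit waning, for example R going from 10 to 0: c = −10, and the gain is understated.

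**Effect on the mean.** If a share f of patients has carry-over c, the mean change shifts by f × c and the SD of differences becomes √(20² + f(1 − f)c²). For f = 25% and c = ±10, the shift is 0.25 × (±10) = ±2.5 points, or 2.5/13 = 19% of the planning difference, and the SD is √(400 + 18.75) = 20.46.

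**Range under assumed inputs.** Neither f nor c is in the documents; the values below are assumptions. The third column takes a true device effect of 0, where the nominal chance of a significant improvement is 2.5%. The last column takes a true device effect of 13, where the nominal power is 86.2%.

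| Share f (patients of 24) | Shift, c = +10 | Chance of a significant improvement, no device effect | Shift, c = −10 | Power for a true 13 |
|---|---|---|---|---|
| 4.2% (1) | +0.42 | 3.1% | −0.42 | 83.6% |
| 12.5% (3) | +1.25 | 4.7% | −1.25 | 77.6% |
| 25% (6) | +2.5 | 8.3% | −2.5 | 67.3% |
| 50% (12) | +5.0 | 20.6% | −5.0 | 44.5% |

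With c = 0 the shift is 0 at every f.

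**The case against.** A reader might infer that the carry-over is simply credited to the device and inflates its 3-month gain. The documents do not support that. Benefit already present at day 0 sits in the baseline CMS; it cancels if stable and reduces the gain if it fades. No section gives a duration of action for PRP or collagen. The cell-culture work in section 2.3 suggests that collagen stimulates tenocytes, and one could argue from it that a recently injected patient would still be improving. But that work is in vitro, on a related product, and gives no clinical time course.

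The other side has further points. Section 2.2 ranks PRP only among biologics, reports mixed results, and says nothing about how often patients at this centre receive it. Prior collagen use is inferred from the post-market label alone. The history-taking row in Table 1 may already pick up earlier injections. And in a 24-patient single-arm pilot, any cause of change after day 0 enters the estimate; closing this gap leaves the others open.

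All of this stands as a limit on the size and direction of the bias. It does not remove the gap. The history-taking row does not ask for product, side or date, excludes nobody, and feeds no analysis. That the design has other unavoidable confounders is no reason to keep one that an existing criterion could remove.

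**Conclusion.** The gap is real: as written, the plan admits patients recently injected in the study shoulder with PRP or a collagen device, and its single-arm, unadjusted paired analysis cannot separate a residual effect from the device effect. The direction is not fixed and the size cannot be computed from the documents. The figure of 2.5 points either way is an illustration that rests on an assumed 25% share, an assumed carry-over of 10 points and additivity with the device effect. If few such patients enrol, or their benefit is stable, the effect is small or nil. The plan's sample size and stated power are not in question.

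**What to change.** In section 3.6.3 and the synopsis, extend the existing exclusion to any recent infiltration of the study shoulder, naming PRP, other biologics and collagen devices, the study device among them. The interval should be set and justified by the sponsor and investigators; nothing in the documents shows that the one used for HA and cortisone suits these products.

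At T0 in section 4.9.2, record all prior injections of the study shoulder by type, side and date, whether or not they count as pharmacological. If the sponsor prefers not to widen the exclusion, this record would at least allow a pre-specified sensitivity analysis without those patients.

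The cost is one changed line in each of the two exclusion lists and one in the visit schedule. A few otherwise eligible patients may be deferred, which could slightly slow the 4-month recruitment. N = 24 and the 86.2% power are unchanged.
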